7.20 Missing data and lost to follow up

To correct for potential differences in between the groups with regard to missing data and patients that are lost to follow up the main analysis will be done with inverse probability weighing (IPW).

7.21 Analysis of secondary outcomes

Antibiotic treatment at follow up

Using linear regression we will compare how many in the intervention and non-intervention group are prescribed antibiotics at the index consultation.

Antiviral treatment at follow up

Using linear regression we will compare how many in the intervention and non-intervention group start antiviral treatment (prescribed or bought over-the-counter) within 14 days after the index consultation.

Reconsultations

Using linear regression we will compare how many in the intervention and non-intervention group come for reconsultations (planned and unplanned) within 14 days after the index consultation.

Hospital referral at index consultation

Using linear regression we will compare how many in the intervention and non-intervention group are referred to hospital at the index consultation.

Hospital admission at follow up

Using linear regression we will compare how many in the intervention and non-intervention group are or have been admitted into hospital until day 14 after the index consultation.

Mortality

Using linear regression we will compare mortality status in the intervention and non-intervention group.

Secondary outcomes will be expressed with 95% two-sided confidence intervals.

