C-reactive protein (CRP) is an acute phase reactant produced by the liver which can be used as a marker of serious infection. Randomised trials of using CRP point of care test (POCT) to guide antibiotic prescription for respiratory tract infections has been successful in lowering unnecessary antibiotic prescriptions in adults in high income countries but left a small concern for safety in the form of possibly slightly increased risk of hospitalisation in the CRP group [14]. Trials of CRP POCT in children have been performed in Tanzania as part of an intervention package with a strict prescription limit of > 80 mg/L CRP with a reduction in antibiotic prescriptions from 40% to 2% [15]. In South-East Asia with a small but statistically significant effect (5% reduction) when used as either above or below a certain threshold (40 mg/L) in Thailand and Myanmar [16]. In a sub-group analysis from a trial in Vietnam with both children and adults where the numeric value of CRP was used after a short training in CRP interpretation along with clinical evaluation resulted in a 20% reduction from 64% to 44% [17]. A cross-cutting qualitative study of the above-mentioned studies in Thailand, Myanmar, and Vietnam showed that lack of non-antibiotic alternatives to prescribe led to lower adherence to the CRP POCT result [18].

As the intervention of supplying CRP POCT to healthcare providers is more a behavioural than biomedical, previous trials have recommended that further trials are done in different contexts and that qualitative studies of reasons for success or failure [17].

Central Asian countries have been underrepresented in health science, especially in primary care research. The clinical context of primary care in South-East Asian countries, like Vietnam, Thailand, and Myanmar, and Central-Asian countries, like Kyrgyzstan, are vastly different with different caseloads, different human resources, and varying time for consultations available [3]. At the same time, case fatality rates for pneumonia in children remain high in Central Asia (Figure 2) and there is a lack of knowledge of which viruses and bacteria cause the disease. Antibiotic resistance patterns of common bacteria remain largely unknown in Central Asia, which makes it challenging for clinicians to choose the right antibiotic to treat children with suspected bacterial pneumonia.

[figure not shown]

Figure 2: Causes of Death in Children under 5 in Central Asia.

COORDINATE

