4.3 Exclusion criteria

COORDINATE

A potential subject who meets any of the following criteria will be excluded from participation in this study:

- Severely ill and in need of urgent referral where measurement of CRP POCT would delay the process;
- Terminally ill patients;
- Patients with ear ache only;
- Patients with known immunosuppression or severe chronic disease (HIV, liver disease, history of neoplastic disease, long term systemic steroid use or similar conditions as assessed by the health worker or AI);
- Parents/caregivers who are not able to participate in follow-up procedures (lack of telephone etc);
- Positive rapid diagnostic test for SARS-CoV-2;
- Haven taken antibiotics within 24 hours before the index consultation

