7.16 Power calculation

As the study employs a combined superiority and non-inferiority approach based on the two related primary study outcomes; we provide two power calculations and opt for the conservative number of participants to ensure the adequate sample size for answering both primary outcomes. Power calculations are performed using sample size calculators provided by Sealed Envelope™.

Superiority power calculations show that for a power of 90% to detect a 10% reduction in antibiotic use (from 55% to 45% based on previous pilot registrations in the area) at a statistical significance level of 0.05 a total of 1046 children, 523 in each arm are necessary.

In our non-inferiority power calculation, we apply a margin of non-inferiority of one day (24 hours), i.e. the intervention arm is allowed to have a mean time to recovery that is one day longer than the mean recovery time in the control arm without being deemed inferior. The duration of acute respiratory tract infection in children is approximately 7 days with a standard deviation of 5 days. Hence, for a power of 90% and a statistical significance level of 0.05 a total of 858 children are needed.

To be able to assess both outcomes we will opt for the conservative measure, e.g. the superiority measure.

With an expected dropout rate of 15% we aim to include 1204 children in total, 602 in each arm. This is deemed achievable with the available resources. We expect to be able to include a sufficient number of patients in approximately three months. Each clinic has a patient flow of approximately 10 – 25 children per week. With 10 clinics, the weekly flow of potential participants is 100 – 250 even if only less than 1 in 2 patients are enrolled; we will still keep this schedule.

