7.22 Adjustment for baseline variables

The analyses of the outcomes will be adjusted for the stratification variables – age and sex – so as to boost the power of the analyses. Additionally, clinical relevant variables such as respiratory frequency, fever and other severity markers will be included.

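### If no child dies, the linear regression planned for mortality gives a 95% CI of 0 to 0, and section 7.21 names no alternative

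*Combined protocol and SAP*

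**What the plan says.** Section 7.15 lists mortality as a secondary outcome, and section 7.10.2 makes death one of the two serious adverse events collected at days 3, 7 and 14. The analysis is in section 7.21: "Using linear regression we will compare mortality status in the intervention and non-intervention group". The same section closes with "Secondary outcomes will be expressed with 95% two-sided confidence intervals". Section 7.22 applies to outcomes generally: "The analyses of the outcomes will be adjusted for the stratification variables", and it adds clinical severity variables. Section 7.23 provides counts and percentages for categorical data, which is descriptive and sets no interval method. Neither the safety and monitoring sections (7.8, 7.10.2, 7.11) nor the analysis sections (7.19 to 7.24) give an exact method, a score method or a descriptive-only rule for mortality.

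The arm sizes come from section 7.16: "we aim to include 1204 children in total, 602 in each arm", of whom "a total of 1046 children, 523 in each arm are necessary" after dropout.

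**The concern.** Linear regression of a yes/no outcome on treatment arm estimates a risk difference, and its interval is serviceable when there are enough events. Its standard error is built from the residual variation in the outcome. With no deaths there is no such variation, so the method reports perfect precision exactly when the data say least about the size of a difference.

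Two features of the protocol bear on how likely that is, and they point in opposite directions. Section 4.3 excludes children who are "Severely ill and in need of urgent referral where measurement of CRP POCT would delay the process", and follow-up lasts 14 days, so deaths may be rare. The introduction, however, says "case fatality rates for pneumonia in children remain high in Central Asia". No expected death rate is stated.

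At stake is how the gravest safety outcome is reported. Section 7.1 requires that fewer antibiotics should not cost patient safety, and the summary names undertreatment of serious disease as a risk. An interval of 0 to 0 would overstate what the trial can say about that risk.

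**Working it through.** **Inputs.** Linear regression and a two-sided 95% CI (7.21); covariates (7.22); 602 per arm enrolled and 523 per arm after dropout (7.16). Death rates are assumed throughout, because the documents give none.

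**The plan's own figure.** There is none for mortality. The arm size can be checked: for 55% against 45%, two-sided 0.05 and 90% power, standard formulas give 521 (unpooled) or 524 (pooled) per arm. Power at 523 per arm is 0.900, so the stated 523 is reproduced.

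**Planned interval.** With x₁ and x₀ deaths, n per arm and p = x/n, the unadjusted regression gives the difference p₁ − p₀ with

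SE = √(s² × 2/n), where s² = [n·p₁(1−p₁) + n·p₀(1−p₀)] / (2n−2).

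- 0 vs 0 deaths: s² = 0, SE = 0, CI = 0 to 0 for any n. Fits with treatment plus four simulated covariates, by ordinary least squares, with HC3 robust errors and with weights, all returned 0 to 0 at both arm sizes.
- 1 vs 0 at n = 602: s² = (601/602)/1202 = 0.000831; SE = √(0.000831 × 2/602) = 0.00166; difference 0.166 points; CI −0.16 to +0.49 points.

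**Score interval (Miettinen-Nurminen) at 0 vs 0.** The limit solves d² = z²·c·d(1−d)/n with c = 2n/(2n−1), so d = z²c/(n + z²c).

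- n = 602: 3.845/605.845 = 0.635 points.
- n = 523: 3.845/526.845 = 0.730 points.

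The Newcombe interval gives ±0.63 and ±0.73, so the result does not depend on the choice of score-type method. The exact upper limit for one arm's risk with no deaths, 1 − 0.025^(1/n), is 0.61% at 602 and 0.70% at 523.

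**Comparison, percentage points**

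| Deaths | n per arm | Planned CI | Score CI | Width ratio |
|---|---|---|---|---|
| 0 vs 0 | 602 | 0 to 0 | −0.63 to +0.63 | 0 |
| 1 vs 0 | 602 | −0.16 to +0.49 | −0.47 to +0.94 | 0.46 |
| 1 vs 1 | 602 | −0.46 to +0.46 | −0.78 to +0.78 | 0.59 |
| 3 vs 0 | 602 | −0.07 to +1.06 | −0.14 to +1.46 | 0.71 |
| 0 vs 0 | 523 | 0 to 0 | −0.73 to +0.73 | 0 |
| 1 vs 0 | 523 | −0.18 to +0.57 | −0.54 to +1.08 | 0.46 |

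**Chance of no deaths**, (1−p)^N at an equal risk p in both arms:

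| Assumed 14-day risk | N = 1204 | N = 1046 |
|---|---|---|
| 0.01% | 89% | 90% |
| 0.05% | 55% | 59% |
| 0.1% | 30% | 35% |
| 0.2% | 9% | 12% |
| 0.5% | 0.2% | 0.5% |

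**Coverage of the planned unadjusted interval**, by summing exact binomial probabilities:

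| Assumed risks | 602 per arm | 523 per arm |
|---|---|---|
| 0.05% vs 0.2% | 0.766 | 0.719 |
| 0.1% vs 0.3% | 0.830 | 0.789 |
| 0.3% vs 0.6% | 0.945 | 0.936 |
| 0.1% in both | 0.996 | 0.998 |
| 0.2% in both | 0.979 | 0.985 |

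Swapping the arms leaves coverage unchanged and moves the misses to the other side. In the first two scenarios the score interval covers between 0.984 and 0.997.

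At 602 per arm the zero-death result accounts for 0.222 of the 0.234 total misses at 0.05% vs 0.2%, and for 0.090 of 0.170 at 0.1% vs 0.3%. Given at least one death, coverage is 0.984 and 0.912 respectively.

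**The case against.** The strongest objection is that this is an edge case with little practical harm. It needs zero or very few deaths, and the assumed range puts the chance of none anywhere from 0.2% to 90%. Counts will be shown under section 7.23, so a reader who sees 0/602 against 0/602 is unlikely to take 0 to 0 at face value, and software may print a missing standard error instead. All of this stands, and it is why the point is minor. It does not supply a usable interval, though, and a method chosen once the deaths are known is no longer prespecified.

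A second objection is that narrower than a score interval does not by itself mean wrong. This also stands in part. With equal risks the planned interval covers above 95%, and the low coverage figures need assumed three- to fourfold differences between arms. Most of the shortfall there is the zero-death case again. The sparse-count problem is therefore secondary.

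A third objection is that a fallback for zero or sparse deaths would be enough, so dropping covariate adjustment at every death count goes further than the fault shown. A fallback would work, but it needs a threshold. One method for every death count is simpler, and with a handful of events adjustment has little to offer. Finally, section 7.20 prescribes weighting only for the main analysis, so it is not a source of the fault; weights matter here only because they would not cure it.

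**Conclusion.** The concern holds. With no deaths, the stated method returns a 95% CI of 0 to 0, while the data would allow a difference of about 0.6 to 0.7 percentage points in either direction. That result is algebraic and rests on no assumption about covariates, variance estimator or arm size. How often it would occur rests on an assumed death rate, which the documents do not supply. With one to three deaths the planned interval is roughly half to seven-tenths as wide as a score interval. It can understate a true difference in either direction if risks are very low and unequal.

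The finding is confined to mortality. Neither primary outcome is affected, and no error is shown for referral, admission or the other secondary outcomes. The change is worth making but optional.

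**What to change.** In section 7.21, for mortality only, replace the linear regression with deaths per arm as n/N and an unadjusted risk difference with a score-type (for example Miettinen-Nurminen) or exact two-sided 95% CI. Name the one chosen, and say which children N counts, since some vital status may be unknown after dropout. In section 7.22, state that mortality is exempt from covariate adjustment. Leave the other secondary outcomes as planned.

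The cost is one sentence in 7.21 and a short exception in 7.22, with no change to data collection or sample size. The drawback is that mortality is compared without adjustment for age, sex or severity.

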7.22 Adjustment for baseline variables

The analyses of the outcomes will be adjusted for the stratification variables – age and sex – so as to boost the power of the analyses. Additionally, clinical relevant variables such as respiratory frequency, fever and other severity markers will be included.

7.23 Presentation of data

Descriptive data will be presented either by means and standard deviations, or medians and interquartile ranges -as appropriate- for continuous data, or by numbers and percentages for categorical data. Data may also be investigated using visual tools (e.g. histogram, box-plot, scatter plot, Kaplan-Meier curves).

7.24 Interim analysis

Since we are planning to include all subjects within two to three months, we do not plan to make an interim analysis. If the inclusion period will be longer than 3 months we will do an interim analysis or when 500 participants are included whichever ever comes first. The interim analysis will assess our primary outcome, safety outcome and adverse events. The PI will present the results of interim analysis to the Data Safety Monitoring Board (DSMB) / Safety Committee (see section 7.11).

8. ETHICAL CONSIDERATIONS

8.1 Regulation statement

The study will be conducted in accordance with the latest version of the principles of the Declaration of Helsinki (64th WMA General Assembly, Fortaleza, Brazil, October 2013), in accordance with the Medical Research Involving Human Subjects Act (WMO) and other applicable privacy laws, local guidelines, regulations and Acts.

The team will ensure the correct regulatory approvals are gained prior to initiation of study. The protocol, and attached documents (ICFs, patient information sheets, CRF and phone questionnaire) will be submitted to an appropriate Research Ethics Committee (REC), and, if needed, additional regulatory authority. If necessary, approvals for all substantial amendments to the original approved documents will be obtained. Any substantial amendment to the protocol must be approved by all collaborating parties before they are submitted for national REC and regulatory approvals.

No patients will be enrolled in a country until all approvals have been obtained for that country's primary care network and sites.

Medical management of participants in this study must never be compromised by study procedures. At all times, priority will be given to samples required for medical management.

8.2 Recruitment and consent

Recruitment

All children presenting or consulting the primary care health clinic for their CA-ARTI symptoms described above can be included in the study. Therefore, the HCWs from primary care health clinics (doctors, nurses, practice assistants and medical students) may be involved in the inclusion procedures.

Screening and Eligibility Assessment

Any child aged from 6 month to 12 years contacting the participating health clinics and who meets the eligibility criteria will potentially be included. Patients will be assessed against the

COORDINATE

inclusion criteria by the HCWs and if eligible, be included upon signing of an IC by their parents/caregivers and have their CRF completed on paper or online.

Informed Consent

When the patient consults at the health clinic, explanation of the study, provision of study-related information, patient information sheet and IC will be performed at the practice. All study personnel will be trained by the national network facilitator or PI, detailing no less than: the exact nature, implications and constraints of the study, and risks and benefits of participation. The study will provide a patient information sheet (appendix B) that includes all necessary information available in the official national language. Half a day will be given to the parents/caregivers to consider the information given to them and to ask any questions they may have about the study to decide whether their child will participate in the study. As participants are not of legal age of consent in their jurisdiction, consent will be provided by their parent/legal guardian. It will be clearly stated in the patient information sheet and verbally explained to the participant that they are free to withdraw from the study at any time for any reason without impacting their future care, and with no obligation to provide the reason for withdrawal.

8.3 Objection by minors or incapacitated subjects

Not applicable

8.4 Benefits and risks assessment, group relatedness

For the children being managed at participating health centres during the intervention period, the study adds a finger prick and, for some, a tracheal swab, which does give some discomfort for the child. On the other hand, it is the intention that the improved diagnosis will lead to better treatment for the child's condition. There is a slight risk that a child has a severe infection with eg. a short prodrome before presenting to the clinician leading to a CRP that is not yet elevated, and if the CRP levels are followed strictly that such a child is not treated with antibiotics. To counter this, part of the training given with the CRP POCT intervention will address such issues and highlight that if the clinician is worried for the child despite a low CRP count, antibiotic therapy should be started. It will also be emphasized that if in doubt, the clinician should re-evaluate the child eg. the next day or what is clinically meaningful. Previous studies very similar to this have shown to be safe for participants.

Sample analyses will become available weeks after the samples were taken, and thereby don't and can't influence patient care or management. Upon request, the national coordinator can supply the sample results to the health clinics after full data analysis, if participants want to inquire their results.

9. ADMINISTRATIVE ASPECTS, MONITORING AND PUBLICATION

9.1 Handling and storage of data and documents

All study-specific documents and laboratory outcomes will be coded with the participant ID, a unique number incorporating the country (one letter K), healthcare centre (two letters) and sequential numbers, so not by name or personal identifiers of the patient. The CRF, swab, contact form and information from phone calls will be identified with this ID. All study documents will be stored securely and only accessible by study staff: PI and designated members of the research team, recruiters in the practices and personnel specifically dedicated for patient follow-up. After completion of follow-up the contact form will be destroyed. The participant code-list (name, birthdate and study ID) will be stored at the healthcare centre.

All paper patient-related documents (ICF, CRF, registration of phone calls) will be stored safely in a locked cabinet in the practice, or office of the PI. The eCRF and electronic entries stored securely at the REDCap online system maintained by the Rigshospitalet and Danske Regioner, Denmark. The REDCap system meets all International Conference on Harmonisation on Good Clinical Practice requirements safeguarding data integrity and electronic data security regulations. Data traffic within REDCap over the internet is encrypted using secured data communication protocols. The central databases and web servers are hosted in a secure data centre. The database (PostgreSQL) is backed up every day. Users will have a role-based access to RO after they log-in using their own personal username and password. This role-based access to the system will avoid unauthorised data access and prevents users from performing actions that they do not have authorisation for. The system logs all data entry steps with timestamps and user information, thereby creating an audit trail. Electronic data will be stored for at least 5 years. See Data Management Plan for further details.

Direct access to source, patient and REDCap data and will be granted to authorised representatives from the Colaborating parties, host institution and the regulatory authorities to permit study-related monitoring, audits and inspections to ensure compliance with regulations. Coded data can be made available for research purposes after permission from the study responsables.

With the procedures described the the personnel dedicated for participant follow-up will ensure that the patients' privacy is maintained.

All documents will be stored securely and are only accessible by the national network coordinator and dedicated study personnel. At the healthcare centres, all staff will safeguard the privacy of patients' personal data.

9.2 Monitoring and Quality Assurance

Monitoring

Monitoring will be implemented as soon as the study starts, checking study procedures, swab taking and storage, patient inclusion and data entry. Central monitoring will be performed by a responsible delegate from Copenhagen University. This procedure will be reviewed as necessary over the course of the study to reflect significant changes to the protocol or outcomes of any monitoring activities.

COORDINATE

No on-site monitoring visits are planned during the study due to the short inclusion period, vast number of clinics and travel constraints. If required health clinics may be monitored at the end of the study, or afterwards by the PI or a responsible delegate.

Quality Assurance Procedures

The study will be conducted and executed in accordance with the approved protocol, and relevant regulations. Prior to starting the study, all study-related staff will be trained in study procedures by the PI and core team. This will include training, delegation of responsibilities, and set-up to the local recruiting health clinics including procedures related to CRP testing.

